6.2.2. Analysis of secondary objective

Descriptive statistics will be provided for each secondary endpoint at each time point for which a sample is available and will include (not exhaustive) the following tabulations (with 95% CI):

- The percentage of CMV seronegative subjects with appearance of anti-CMV tegument protein IgG antibodies in serum.

6.2.3. Analysis of Tertiary objective

Descriptive statistics will be provided for the number of CMV DNA copies in urine at each time point for which a sample is available and the percentage of CMV seronegative subjects with presence of CMV DNA in urine will be tabulated (with 95% CI).

For all results of assays performed for the further characterization of primary and/or secondary CMV infections, descriptive statistics will be provided for each assay at all selected time points for which a sample is available.

The analysis of tertiary objectives will be described in an analysis plan amendment (before unblinding) or in an additional analysis request (after unblinding).

For further details on standard business rule for GMT computation, see annex 1.

7. ANALYSIS INTERPRETATION

All analyses are descriptive. The use of these descriptive analyses should be limited to supportive analysis of confirmatory analyses or hypothesis generation.

8. CONDUCT OF ANALYSES

8.1. Sequence of analyses

Description	Analysis ID	Disclosure Purpose (CTRS=public posting, SR=study report, internal)	Dry run review needed (Y/N)	Study Headline Summary (SHS)requiring expedited communication to upper management (Yes/No)	Reference for TFL
Analysis of epoch 001	E1_01	Study report			All tables from TFL dated
Analysis of epoch 001	E1_02	Study report			All tables need to be detailed

9. LIST OF FINAL REPORT TABLES, LISTINGS AND FIGURES++++

Listing of TFL and Mock TFLs can be found in the document “CMV 014 (115639) TFL”

10. ANNEX 1 STANDARD DATA DERIVATION RULE AND STATISTICAL METHODS

10.1. Statistical Method References

The exact two-sided 95% CIs for a proportion within a group will be the Clopper-Pearson exact CI [Clopper CJ, Pearson ES. The use of confidence or fiducial limits illustrated in the case of binomial. *Biometrika*. 1934;26: 404-413]. The standardised asymptotic two-sided 95% CI for the group difference in proportions is based on the method described in the following paper: Robert G. Newcombe, interval estimation for the difference between independent proportions: comparison of eleven methods, *Statist Med*. 1998; 17, 873-890]. The standardised asymptotic method used is the method six.

10.2. Standard data derivation

GSK legacy

- SAS date derived from a character date: In case day is missing, 15 is used. In case day& month are missing, 30June is used.
- Onset day for an event (ae, medication, vaccination, ...): The onset day is the number of days between the last study vaccination & the onset/start date of the event. This is 0 for an event starting on the same day as a vaccination. See SAS date derived in case the start date of the event is incomplete.
- Duration: Duration of an event is expressed in days. It is the number of days between the start & the stop dates + 1. Therefore duration is 1 day for an event starting & ending on the same day.
- Association of an event to the primary epoch: An adverse event belongs to the primary epoch, if the onset date is before and excluding Visit 5 or the last contact date, whichever is coming first.
- Not applicable
- Age: Age at the reference activity, computed as the number of units between the date of birth and the reference activity. Note that due to incomplete date, the derived age may be incorrect by 1 month when month is missing from the birthdate. This may lead to apparent inconsistency between the derived age and the eligibility criteria/the age category used for randomization.
- Conversion of weight to kg
The following conversion rule is used:
 - Weight in Kilogramm= weight in Pounds / 2.2
 - Weight in Kilogramm =weight in oncs / 35.2The result is rounded to 2 decimals.

- Conversion of height to cm

The following conversion rule is used:

- Height in Centimetres = Height in Feet * 30.48
- Height in Centimetres = Height in Inch * 2.54

The result is rounded to the unit (ie no decimal).

- Conversion of temperature to °C

The following conversion rule is used:

- Temperature in °Celsius = ((Temperature in °Fahrenheit -32) *5)/9

The result is rounded to 1 decimal.

- For a given subject and given immunogenicity measurement, missing or non-evaluable measurements will not be replaced. Therefore, an analysis will exclude subjects with missing or non-evaluable measurements.

- The Geometric Mean Concentrations/Titres (GMC/Ts) calculations are performed by taking the anti-log of the mean of the log titre transformations. Antibody titres below the cut-off of the assay will be given an arbitrary value of half the cut-off of the assay for the purpose of GMT calculation. The cut-off value is defined by the laboratory before the analysis and is described in the protocol.

- A seronegative subject is a subject whose antibody titre is below the cut-off value of the assay. A seropositive subject is a subject whose antibody titre is greater than or equal to the cut-off value of the assay.

- The assay cut-off is the value under which there is no quantifiable result available. For an assay with a specific ‘cut_off’ , numerical immuno result is derived from a character field (rawres):

- If rawres is ‘NEG’ or ‘-’ or ‘(-)’, numeric result= cutt_off/2,
- if rawres is ‘POS’ or ‘+’ or ‘(+)’, numeric result = cut_off,
- if rawres is ‘< value’ and value<=cut_off, numeric result =cut_off/2,
- if rawres is ‘< value’ and value>cut_off, numeric result =value,
- if rawres is ‘> value’ and value<cut_off, numeric result =cut_off/2,
- if rawres is ‘> value’ and value>=cut_off, numeric result =value,
- if rawres is ‘<= value’ or ‘>= value’ and value<cut_off, numeric result =cut_off/2,
- if rawres is ‘<= value’ or ‘>= value’ and value>=cut_off, numeric result =value,
- if rawres is a value < cut_off, numeric result = cut_off/2,
- if rawres is a value >= cut_off, numeric result = rawres,
- if rawres is a value >= cut_off, numeric result = rawres,
- else numeric result is left blank.

- All CI computed will be two-sided 95% CI.

- Not applicable; only SAE Listings will be provided

Number of decimals displayed:

The following decimal description from the decision rules will be used for the demography, immunogenicity and safety/reactogenicity.

Display Table	Parameters	Number of decimal digits
Demographic characteristics	Mean, median age	1
Demographic characteristics	SD (age)	1
Immunogenicity	Ratio of GMT/C	2
Reactogenicity	Mean, Min, Q1, Median, Q3, Max for duration	1
All summaries	% of count, including LL & UL of CI	1
All summaries	% of difference, including LL & UL of CI	2
All summaries	p-value	3

CONFIDENTIAL

115639 (CMV-014 EXPLO)
Statistical Analysis Plan-Draft

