5.4. Outline of study procedures

Table 2 List of study procedures (amended 19 February 2015)

Age	10-17 years							
Epoch	001							
	Year 1							
Time-point (Months)	M0	M2	M4	M6	M8	M10	M12	
Visit/Sample Collection Visit	V1	SCV1	V2	SCV2	V3	SCV3	V4	
	Year 2							
Time-point (Months)		M14	M16	M18	M20	M22	M24	
Visit/Sample Collection Visit		SCV4	V5	SCV5	V6	SCV6	V7	
	Year 3							
Time-point (Months)		M26	M28	M30	M32	M34		M36
Visit/Sample Collection Visit		SCV7	V8	SCV8	V9	SCV9		V10
Informed consent	●							
Check inclusion/exclusion criteria	●							
Record demographic data	●							
Record social and behavioral data ⁽¹⁾	●						●	●
Medical history	●							
CMV serostatus ⁽²⁾ (~3.5 to 5 mL)	●							
Blood sample ⁽³⁾								
- for humoral immunity (10 mL)	●		●		●		●	●
- for molecular biology (4 mL)								
Blood sample for gene expression signature (qPCR or RNA microarray; 2.5 mL) ⁽⁴⁾	●						●	
Urine sample ⁽⁵⁾ (~10 mL)	●	●	●	●	●	●	●	●
Saliva	●	●	●	●	●	●	●	●
Subject sample collection booklet distribution ⁽⁶⁾	○							
Check elimination criteria	●		●		●		●	●
Record any concomitant medication/vaccination ⁽⁷⁾	●		●		●		●	●
Reporting of SAEs related to study participation	●		●		●		●	●
Reporting of pregnancy and outcome	●		●		●		●	●
Study conclusion								●

● is used to indicate a study procedure that requires documentation in the individual eCRF.

○ is used to indicate a study procedure that does not require documentation in the individual eCRF

⁽¹⁾ Social and behavioral data will be recorded at inclusion (Visit 1 [Month 0]), at Visit 4 (Month 12), Visit 7 (Month 24) and Visit 10 (Month 36).

⁽²⁾ CMV serostatus, for allocation to a study group (S+ or S-), will be determined by the local laboratory as per local practices or by a GSK designated and validated central laboratory.

⁽³⁾ CMV serostatus for endpoints analysis will be determined by GSK Biologicals or designated laboratory at Visit 1 (Month 0).

⁽⁴⁾ **These blood samples will be collected until approval of protocol amendment 2.**

⁽⁵⁾ Prepared from the 20 mL urine samples collected from the subject.

⁽⁶⁾ The sample collection booklet will instruct the subjects of the study procedures to be performed at the Sample Collection Visits. The sampling can be done through self-collection, through a home-visiting nurse or the subject may be asked to come back to the study center.

⁽⁷⁾ Only concomitant medication/vaccination related to inclusion/exclusion and elimination criteria will be recorded.

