8.5. Derived and transformed data

Immunogenicity

The cut-off value is defined by the laboratory before the analysis and is described in [Table 6](#).

- A seronegative subject is a subject whose titer is below the cut-off value.
- A seropositive subject is a subject whose titer is greater than or equal to the cut-off value.

For seronegative subjects, seroconversion is defined as the appearance of antibodies (i.e. titer greater than or equal to the cut-off value).

The geometric mean titers (GMTs) calculations will be performed by taking the anti-log of the mean of log titer transformations. Antibody titers below the cut-off of the assay will be given an arbitrary value of half the cut-off for the purpose of GMT calculation.

Virology

For seronegative subjects, CMV DNAemia is defined as the detection of CMV DNA (i.e. number of CMV DNA copies/mL is greater than or equal to the cut-off value).

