6.2. Objectives

6.2.1. Analysis of primary objective

Descriptive statistics will be provided for each primary endpoint at all available time-points and will include (not exhaustive) the following tabulations (with 95% confidence interval [CI]):

- The percentage of CMV seropositive subjects with increase of anti-CMV tegument protein IgG antibodies in serum. An increase will be defined by both a 2-fold or greater increase *and* separately a 4-fold or greater increase in the anti-tegument antibody concentration between subject visits or the last available anti-tegument antibody value if the subject missed a visit or serological results are unavailable.
- The percentage of CMV seropositive subjects with appearance or increase of CMV DNA in urine. A reactivation/reinfection event, based on DNA in the urine, will be defined as any one of the following : (1) the appearance of any detectable CMV DNA by PCR in a sample if CMV DNA was not detected in the previous sample for that subject (2) if the previous sample had CMV DNA detected, but was below the LLOQ for the assay, any value above the LLOQ will be considered a reactivation/reinfection event; and (3) if the previous sample result was above the LLOQ, an increase $\geq 0.5 \log_{10}$ CMV DNA copies/mL in the subsequent sample will be considered an event. It is expected that CMV-positive subjects may have more than one reactivation/reinfection event during the follow up period in this study.

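### SAP Annex 1 turns out-of-range IgG results into exact numbers, so sera of undetermined status are scored positive or negative, and rises from a prior value above half (2-fold) or a quarter (4-fold) of the upper assay limit are missed

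*SAP*

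**What the plan says.** SAP 10.2 lists, under a heading marking the rules as company legacy, how a raw laboratory entry becomes a number. Three lines matter here:

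- over-range: "if rawres is ‘> value’ and value>=cut_off, numeric result =value"
- an upper bound above the cut-off: "if rawres is ‘< value’ and value>cut_off, numeric result =value"
- a lower bound below the cut-off: "if rawres is ‘> value’ and value<cut_off, numeric result =cut_off/2"

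Serostatus is read from the derived number: "A seropositive subject is a subject whose antibody titre is greater than or equal to the cut-off value of the assay". For girls negative at entry, Protocol 8.5 states that "seroconversion is defined as the appearance of antibodies (i.e. titer greater than or equal to the cut-off value". The analysis group also depends on this assay result, because under the procedures table in Protocol 5.4 "CMV serostatus for endpoints analysis will be determined by GSK Biologicals or designated laboratory at Visit 1 (Month 0".

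The primary IgG tabulation in SAP 6.2.1 is "The percentage of CMV seropositive subjects with increase of anti-CMV tegument protein IgG antibodies in serum". It adds: "An increase will be defined by both a 2-fold or greater increase", with a 4-fold version tabulated separately. Each value is compared with the previous visit, or with the last available value if a visit or result is missing.

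The opening note of SAP section 6 says the Annex 1 derivation rules govern the analyses that follow. The half-cut-off substitution is described as being for GMT calculation. The raw-field list carries no such limit.

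**The concern.** Replacing a censored result by a single number is a usual convenience for a geometric mean. It is less safe for a threshold decision, and both uses here are threshold decisions: at or above the cut-off, and at or above a 2-fold or 4-fold ratio.

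At the lower end, the list gives a '< value' result the largest number it could be, and gives a '> value' result below the cut-off a number that makes it negative. Either way an unknown status is reported as known. At Visit 1 this can place a girl in the wrong objective's denominator. Later it can create or hide a seroconversion.

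At the upper end, the ratio is capped. A girl with a high prior value in an interval cannot register a rise in that interval, yet counts there as a non-event. The study population is selected to include many girls who already carry antibody, so high prior values are a natural possibility. All analyses are descriptive (SAP section 7), so these percentages and their intervals are the study's main product.

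**Working it through.** **The plan's own figure.** Protocol 8.2 expects about 12 re-infected seropositive girls from 200 evaluable, 2% per year and 3 years: 200 × 0.02 × 3 = 12.0; compounding gives 200 × (1 − 0.98³) = 11.76. Both reproduce it. Nothing below disputes it; it only sets the scale.

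**What the rules do.** The documents give no range for the tegument ELISA. For illustration take a cut-off of 10 and U = 1000.

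| Prior | Next | Derived ratio | 2-fold | 4-fold |
|---|---|---|---|---|
| >1000 (true 1200) | >1000 (true 6000) | 1000/1000 = 1.0 | no | no |
| 600 | >1000 (true 3000) | 1000/600 = 1.67 | no | no |
| 400 | >1000 (true 2000) | 1000/400 = 2.5 | yes | no |
| 240 | >1000 (true 1200) | 1000/240 = 4.17 | yes | yes |
| 12 | <50 | 50/12 = 4.17 | yes | yes |

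The first four rows are all true 5-fold rises. With prior value b, the largest ratio the rule can return is U/b. A true rise is therefore lost on the 2-fold test only if b > U/2, and on the 4-fold test only if b > U/4. The last row goes the other way: the true second value may be lower than 12, yet a 4-fold rise is recorded.

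For serostatus at the same cut-off, '<20' becomes 20 and '<40' becomes 40, both seropositive, although the titre may be under 10. A negative serum followed by '<20' counts as seroconversion. '>5' becomes 5 and is seronegative, although the titre may be above 10. The '<=' and '>=' lines behave alike ('<=20' is positive, '>=5' negative).

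**Possible size of the upper-end effect, by assumption only.** Suppose log10 titres are normal with SD 0.5 and a share q of prior values lies above U. The share of true rises missed in one interval is P(b > U/k) = 1 − Φ(z − log10(k)/0.5), where z is the (1 − q) normal quantile and k is 2 or 4. At q = 10%, z = 1.28:

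- k = 2: 1 − Φ(1.28 − 0.60) = 25%
- k = 4: 1 − Φ(1.28 − 1.20) = 47%

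| q | 2-fold rises missed | 4-fold rises missed |
|---|---|---|
| 0% | 0% | 0% |
| 5% | 15% | 33% |
| 10% | 25% | 47% |
| 30% | 53% | 75% |

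On the plan's scale at q = 10%, 12 true rises become 12 × 0.75 = 9. The 2-fold percentage falls from 12/200 = 6.0% (Clopper-Pearson 95% CI 3.1 to 10.2) to 9/200 = 4.5% (2.1 to 8.4).

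**Would dropping indeterminate intervals cure this?** Keep q = 10% and SD 0.5, with 6% true 5-fold rises and no change in the rest. Recorded 2-fold events are 6% × (1 − 0.248) = 4.5%. Indeterminate intervals are all those starting above U, plus the rises starting between U/2 and U: 10% + 6% × (0.248 − 0.10) = 10.9%. Dropping them gives 4.5/(100 − 10.9) = 5.1%. Of the shortfall of 6.0 − 4.5 = 1.5 points, 0.9 remains. A girl with a prior value between U/2 and U stays in as a non-event if she does not rise and leaves if she does, so exclusion depends on the outcome. Bounds are honest but wide: 4.5% with all indeterminate intervals as non-events, and 4.5 + 10.9 = 15.4% with all as events.

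**The case against.** The strongest reply is that nothing shows the rules will be triggered. The list is generic legacy text, alongside vaccination onset days and temperature conversion that have no role here. Protocol Table 6 leaves the tegument cut-off to be determined, no upper limit is stated, and the laboratory may titrate to an end point and never issue '<' or '>' results. The annex also describes the cut-off as the level below which no quantifiable result exists, so a '< value' result above it may be rare. All of this stands: the size cannot be derived from the documents, and nil is possible. It does not remove the defect, because the rules are written to apply and give a wrong answer whenever they do. SAP 6.2.1 sets explicit quantification-limit rules for urine DNA but none for IgG.

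Four stronger readings are tempting and are not supported:

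- **That every rise beyond the assay range scores as no increase.** A rise into the over-range still counts if the prior value is at or below U/2 or U/4.
- **That a share of girls can never meet the criterion.** The comparison is made interval by interval, up to nine per girl over ten Site Visits. A high value blocks that interval only.
- **That each affected serum in a seronegative girl is a false primary infection.** Her titre may really be above the cut-off, and repeated sera are not separate infections.
- **That the bias runs one way.** The '<' and mirror rules can push rises and serostatus in either direction.

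**Conclusion.** The point holds in limited form. As written, SAP 10.2 scores some undetermined sera as definitely positive or negative, and can record a false fold rise from a '<' result. It also misses true rises within an interval when the prior value exceeds U/2 or U/4, so the 4-fold tabulation is hit harder. No other text in either document flags such IgG results, makes them non-evaluable or requires repeat dilution for this assay.

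The size is unknown. The percentages above rest on an assumed share of over-range values and an assumed log-normal spread; they are per interval and are zero if the laboratory reports no such results. The urine DNA endpoint has its own rule and is not touched. The change is worth making because it is cheap and, with about 12 events expected, a few misclassified intervals would show.

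**What to change.** In SAP 10.2, limit the raw-field substitutions to GMC/GMT, and add rules for the threshold endpoints:

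1. State the tegument ELISA cut-off and upper limit, and whether the laboratory reports '<' or '>' results. SAP 10.2 refers to the protocol for the cut-off, where it is still open.
2. For serostatus and seroconversion, set '< value' with the value above the cut-off, and '> value' with the value below it, to undetermined (blank). Treat the '<=' and '>=' lines likewise. Do not use such results as exact values in a fold ratio. This fits the annex's own principle that non-evaluable measurements are not replaced.
3. For intervals involving '>U', score an event when the lower bound of the ratio reaches the threshold. An over-range value followed by an in-range one is a certain non-event. Flag the remaining intervals as indeterminate.
4. Report the number of indeterminate intervals, and show the percentage with all of them as non-events and with all as events. Do not rely on dropping them alone.

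Where stored serum allows, re-assay at a higher dilution is the only step that recovers the missing rises. Protocol 5.6 provides for storage for up to 15 years.

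The cost is a short SAP amendment and a few programming lines. The downside is an estimate shown with bounds, which may be wide if many results are over range.

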6. STATISTICAL ANALYSES

Note that standard data derivation rules and statistical methods are described in annex 1 and will not be repeated below.

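### SAP 10.2 sets IgG results below the cut-off to half the cut-off, so a seropositive subject's return across it always counts as a 2-fold increase

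*SAP*

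**What the plan says.** SAP section 6 brings Annex 1 into its analyses: "standard data derivation rules and statistical methods are described in annex 1". Within that annex, SAP 10.2 derives the numeric antibody result from the raw laboratory field. The branch that matters is "if rawres is a value < cut_off, numeric result = cut_off/2". Qualitative negatives, and 'less than' results at or below the cut-off, also become half the cut-off. A numeric result at or above the cut-off is kept as reported, and a bare positive becomes the cut-off itself.

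The same section also describes the substitution as "an arbitrary value of half the cut-off of the assay for the purpose of GMT calculation", and Protocol 8.5 says that such titres "will be given an arbitrary value of half the cut-off for the purpose of GMT calculation". It further states: "The assay cut-off is the value under which there is no quantifiable result available".

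For the primary objective, SAP 6.2.1 tabulates "The percentage of CMV seropositive subjects with increase of anti-CMV tegument protein IgG antibodies in serum". The rule is "An increase will be defined by both a 2-fold or greater increase", with a separate 4-fold version. The comparison is with the previous visit, or with the last available value if that visit has no result. No comparator is named for an IgG value below the cut-off. For urine DNA the same section does set one, with separate rules for a previous sample that was undetected and for the case "if the previous sample had CMV DNA detected, but was below the LLOQ for the assay". The urine row covers appearance as well as increase. The IgG row covers only increase, although Protocol 8.3 and 8.7.2 use both words for IgG. SAP 5.3 also builds subgroup sets on the two-fold and four-fold IgG rises.

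**The concern.** Half the cut-off is a placeholder. It is harmless in a geometric mean but not as the denominator of a ratio whose threshold is exactly 2. Once it feeds the fold-rise, every return across the cut-off passes the 2-fold test by construction. A subject whose stable titre lies just above the cut-off can produce this through assay variation alone.

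The 2-fold IgG row is one of the primary-endpoint tabulations, and the same event selects subjects for a SAP 5.3 subgroup. Both would carry the label of a 2-fold increase while including subjects in whom no such rise was measured. Because SAP 6.2.1 drops appearance for IgG, a re-crossing has no other row to go to.

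**Working it through.** **Inputs.** Derivation rules: SAP 10.2. Thresholds (2-fold and 4-fold, both inclusive) and comparator: SAP 6.2.1. Population: subjects seropositive at Visit 1 (Protocol glossary; serostatus for analysis comes from the sponsor's or designated laboratory, Protocol section 3). Evaluable subjects: about 200 (Protocol 8.2). The tegument IgG cut-off is still to be determined (Protocol Table 6); call it c. It cancels below.

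**The plan's own figure.** Protocol 8.2 expects about 12 re-infected subjects: 200 × 0.02 × 3 = 12.0, or 200 × (1 − 0.98³) = 11.8. It reproduces. The point does not depend on it, but it gives the scale: 12/200 = 6.0%.

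**Step 1: possible derived values.** Under SAP 10.2 each non-blank derived result is either exactly c/2 or at least c.

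**Step 2: ratio on return.** Derived ratio = next value ÷ (c/2) = 2 × (next value/c). As the next value is at least c, the ratio is at least 2 for any c.

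| Raw change | Raw ratio | Derived ratio | 2-fold row | 4-fold row |
|---|---|---|---|---|
| 0.99c to 1.00c | 1.01 | 2.0 | counted | no |
| 0.95c to 1.05c | 1.11 | 2.1 | counted | no |
| 0.80c to 1.10c | 1.38 | 2.2 | counted | no |
| 1.01c to 1.02c | 1.01 | 1.01 | no | no |
| 0.99c to 2.00c | 2.02 | 4.0 | counted | counted |
| 0.10c to 1.50c | 15 | 3.0 | counted | no |

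The 4-fold row is not automatic: it needs a return to at least 2c.

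**Step 3: the combined row.** Pairs of values both at or above c are untouched by the substitution. Pairs both below c have derived ratio 1. All upward crossings count. So the 2-fold row under the substitution equals upward crossings plus 2-fold rises between two quantifiable values. That is Protocol 8.7.2's appearance-or-increase percentage, with increase taken at 2-fold. The substitution adds nothing to it.

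**Step 4: size per subject.** 1/200 = 0.5 percentage points.

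**Step 5: how many subjects.** The documents give no assay CV or titre distribution, so this step is assumption only. Assume a stable titre, no infection, log-normal error with σ = √(ln(1 + CV²)), ten visits, Visit 1 at or above c, and medians spread evenly over 1.1c to 1.5c. The simulated percentage of such subjects with at least one 2-fold increase (600,000 subjects per CV) is:

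| CV | Half cut-off | Measured values | Cut-off as comparator |
|---|---|---|---|
| 10% | 14.4 | 0.0 | 0.0 |
| 15% | 33.5 | 0.4 | 0.2 |
| 20% | 52.9 | 5.4 | 2.4 |
| 25% | 68.8 | 18.1 | 9.1 |

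The excess over measured values is 14.4/33.0/47.5/50.7 points. It is 12.5/29.0/42.7/47.0 with 15% of later visits missing, and 8.5/19.6/30.4/38.0 with within-subject error correlation 0.5. The full range of excess is thus 8.5% to 50.7%. If 10 of 200 subjects lay in that band (assumed), this is 0.85 to 5.07 extra subjects, or 0.4 to 2.5 points. If 2 did, it is 0.17 to 1.01 subjects, or 0.1 to 0.5 points. Against the cut-off as comparator the largest excess is 59.7%, so 10 subjects would give 5.97, or 3.0 points. For a median of 2c the excess over measured values is at most 0.6 points. The 4-fold row was reached by at most 4.8% of near-cut-off subjects.

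**The case against.** **The combined row is right.** Protocol 8.3 and 8.7.2 ask for appearance or increase, and a return across the cut-off is naturally read as appearance. The 2-fold row as written gives that quantity (step 3). This stands. A reader might infer that the protocol's primary percentage is inflated; it is not. The fault is that re-crossings are labelled as 2-fold increases and enter the two-fold set under that name.

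**Scope.** Both explicit statements of purpose tie half the cut-off to GMTs, and SAP 6.2.1 does not say that derived values feed the fold-rise. A reader might infer that SAP 10.2 contradicts itself or the protocol. It does not: the raw-field rules are wider than those sentences, not opposed to them. But the SAP defines no other numeric IgG variable, so the wider rule is the one a programmer would follow.

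**Values below the cut-off.** The SAP says nothing there is quantifiable, so the true size of a re-crossing may be unknowable, and the raw ratios in step 2 and the measured-values column in step 5 are illustrations. This limits how small one may say the change was. It does not support calling the change 2-fold.

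**Display.** SAP 6.2.1 calls its list not exhaustive, and the table shells are in a separate document not available here. A reader might infer that re-crossings could never be told apart in the report; that is unproven.

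**Noise and convention.** Under the same kind of assumptions at CV 20–25%, assay noise alone puts about 6–20% of subjects at 2 to 10 times the cut-off in the 2-fold row, with or without the substitution. Choosing c over c/2 as comparator is also partly convention. Both stand: the first limits what the change can achieve, and the second is why one comparator should not be presented as the only acceptable one.

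**Conclusion.** Wrong as written, but minor. The mechanism follows from SAP 10.2 and 6.2.1 whatever the cut-off: a seropositive subject's return from below always scores at least 2 and enters the 2-fold row and the SAP 5.3 two-fold set without a demonstrated 2-fold rise.

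The mechanism is certain; its total effect is not. How many subjects cross and return depends on the assay CV and on how many titres lie near the cut-off. The documents give neither, so the step 5 percentages should not be read as estimates for this study. The total may be near zero. No test or decision rule is affected: SAP section 7 makes every analysis descriptive and limits its use to support or hypothesis generation.

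**What to change.** In SAP 10.2, state that the half-cut-off value is for GMT/GMC and does not by itself define a fold-rise, and carry a below-cut-off flag into the fold-rise derivation.

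In SAP 6.2.1, restore appearance for IgG, as already done for urine DNA:
- an appearance row for returns from below to at or above the cut-off;
- 2-fold and 4-fold rows kept for rises that the assay can demonstrate;
- the combined row of Protocol 8.7.2.

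One acceptable definition of a demonstrable rise takes the cut-off as comparator, so that a later value of at least 2 or 4 times the cut-off is needed. In SAP 5.3, state which row defines the two-fold set.

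The cost is a few SAP lines and two table rows, unless the table shells already contain them. No samples or tests are added. The downside is that some true rises from well below the cut-off, such as 0.3 to 1.5 times the cut-off, would appear under appearance and not in the 2-fold row. With the cut-off as comparator, a rise from below that ends at 2 to under 4 times the cut-off would count as 2-fold but not 4-fold. None leaves the combined row. The change relabels events; it does not remove assay noise from the combined row.
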